APPENDIX 2 - Schedule of Assessments for Participants Who Progress to Stage 3 T1D

	Initial ¹				
Month		6	12	18	24+ ⁶
Visit Window	+/- 7 days	+/- 14 days	+/- 14 days	+/- 14 days	+/- 14 days
Directed Physical Exam	X	X	X	X	X
Intensive Diabetes Management Review	X	X	X	X	X
MMTT ²	X	X	X	X	X
HbA1c ²	X	X	X	X	X
Concomitant Medication	X	X	X	X	X
Adverse Event Assessment	X	X	X	X	X
Urine Pregnancy Test	X	X	X	X	X
Mechanistic Assessments ³	X	X	X	X	X
Unblinded CGM Wear ⁴	X	X	X	X	X
Fecal Sample ⁵					

1. Initial Visit: To occur within 12 weeks from date of diagnosis of Stage 3 T1D
2. MMTT to be performed only when residual C-Peptide is evident at last available MMTT result. If c-peptide is no longer detectable at last available MMTT result, the participant will no longer complete MMTTs. From this point, the participant will only complete the other visit assessments, including HbA1c, which can be done in-person or remotely. Some individuals with c-peptide may decline undergoing MMTT visits but still wish to participate in the study. In this case visit assessments may be obtained in person or remotely.
3. Samples may be obtained for mechanistic studies developed to address the aims of this protocol, including RNA, plasma, serum, DNA, and/or measures of immune cell number and function. At no time will blood volume exceed what is allowable per the participant's age and body weight (5 mL/kg per day and 9.5 mL/kg over an 8-week period for children under age 18).
4. Unblinded CGM wear for 7-10 days will occur after each visit in the Stage 3 T1D schedule.
5. If participant is diagnosed with Stage 3 T1D <1 year after baseline (V0), fecal sample can be collected at a stage 3 visit if the visit occurs 3 months \pm 7 days and/or 12 months \pm 14 days after baseline (window based on the Stage 2 schedule for V3 and V5).
6. The bi-annual schedule will continue as long as follow-up continues within the scope of this trial.

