5.3 Mechanistic Outcome Assessments

TrialNet will perform immune and genetic assays to further understand mechanisms that may be underlying the type 1 diabetes disease process and response to therapy. TrialNet proposes to evaluate the relationships between changes in immune cells and the delay in onset of T1D. Transcriptomic and serologic studies are planned. In addition, the relationship between specific genotypes and the responses to ATG may be explored. For these purposes, samples for PMBC, DNA, RNA, plasma, and serum may be obtained. The following HLA typing will also be performed: Class I (HLA-A, B, and C) and Class II (DRB, DQA, DQB).

Fecal samples will also be collected from willing participants to explore whether the gut microbiome can predict response to therapy and whether therapy induces changes in the microbiome.

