5.5 Visit Windows

Randomization and the baseline visit must occur within 7 weeks (52 days) of having met two or more of the high-risk markers. All subsequent treatment visits and follow up visits in Appendix 1 must occur within the time limits specified below:

Visit Windows	
Visit -1:	Open window for screening for any participants with 2+ Antibodies
Visit 0:	Randomization within 7 weeks (52 days) of having met ADA Stage 2 criteria and at least one of the high-risk markers. First dose of ATG/placebo given over minimum of 6 hours and maximum of 10 hours. The infusion can be slowed or temporarily stopped to treat signs or symptoms of cytokine release with a maximum infusion time for each infusion of 10 hours.
Visit 1:	The second dose should be given no earlier than 12 hours and no later than 30 hours from the start of the first infusion. The second infusion of ATG/placebo given over a minimum of 6 hours and maximum of 10 hours. The infusion can be slowed or temporarily stopped to treat signs or symptoms of cytokine release with a maximum infusion time for each infusion of 10 hours.
Visits 1.1-1.3*	PK samples should be drawn on target days 2 and 4. Window for day 7 PK draw is ± 1 day.
Visit 2:	± 3 days

Visits 3:	± 7 days
Visits 4 to 13:	± 14 days

*subset of participants, as detailed in section 5.2.1.

5.5.1 Visit Window for Participants who Progress to Stage 3

Once a participant has reached primary endpoint (Stage 3 T1D), the participant will continue study visits according to Appendix 2. The initial study visit is to take place within 12 weeks from date of diagnosis. Study visits will then be completed every six months and within ± 14 days from the target date. The target date will be calculated from the date of the participant's initial visit post diagnosis of stage 3 T1D (1st MMTT visit). Participants who develop diabetes will be followed for a minimum of 1 year. Once follow-up within this study has finished, participants have the option to be followed in TrialNet's LIFT protocol for monitoring or other studies that are available.

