8.4 Sample Size and Power Calculations

This study has been designed to provide at least 85% power to detect a 60% risk reduction in the hazard rate for progression from Stage 2 (with a 50% 2 year progression risk) to Stage 3 T1D using a two-sided test at the 0.05 level once the targeted number of Stage 3 T1D's have been observed. We note that if accrual is more rapid than expected, minimum follow-up on participants may need to be extended or additional accrual in order to meet the number of events required for the final analysis.

A total of 101 participants will be randomized in a 2:1 allocation to treatment with low-dose ATG vs. placebo (e.g., 68 and 33, respectively). Randomization will be conducted using block randomization with variable block sizes.

The assumptions underlying the estimated sample size for this design are: (1) a detectable hazard ratio of 0.4, (2) a minimum of 2 years of follow-up on all participants who have not progressed to Stage 3 T1D, (3) an accrual period of approximately 4 years, and (4) less than a 10% two-year dropout rate in both groups. Under the above assumptions, the target total number of events is equal to 44 assuming the alternative hypothesis; i.e., the final analysis will be conducted once 44 events (Stage 3 T1D diagnosis) have been observed.

With this augmented eligibility criteria and based on the TrialNet Pathway to Prevention (PTP) data (TN01), we would expect to have on average 20 participants per year aged 6 to 35 years old identified with two or more of the high-risk features described in the eligibility criteria.

The final test of significance will employ group sequential critical values to protect against inflation in the type I error probability due to interim assessments of the emerging data for review by the DSMB (see Section 8.5).

Note the accrual period and the study sample are only projections, and the actual accrual rate and the loss-to-follow-up rate are unknown. As the study progresses, more accurate projections of the study end date will be computed based on the observed rate of enrollment, the observed number of events, and the observed rate of loss-to-follow-up. These data will be provided to the DSMB and the TrialNet governing body, and if need be, this document will be amended to reflect revised planning parameters.

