- ATG Drug Induced Antibodies (DIA): Samples will be drawn on 12 participants in each of the following age groups: <18 years and ≥ 18 years at randomization. Pre-infusion sample will be drawn on Day 0. Samples will also be drawn on Days 4 and 7, Week 2, and Month 3.
- May include samples for RNA, plasma, serum, DNA, measures of B and T cell number and function to understand the effect of therapy on the immune system and infectious disease. The following HLA typing will also be performed: Class I (HLA-A, B, C) and Class II (DRB, DBA, DQB). The schedule for these assessments may vary as appropriate. At no time will the blood draw volume exceed what is allowable according to the participant's age and body weight (for participants <18 years, 5 mL/kg per visit, 9.5 mL/kg in an 8-week period).
- Contact with participant every other day will occur once the study treatment is complete until the 2-week visits. Following the 2-week visit weekly contact with participant will occur until the 3-month visit. Contact thereafter will occur every 3 months, in-between in person study visits to assess for symptoms of diabetes and changes in health. Participants who report signs/symptoms consistent with Stage 3 T1D will be asked to complete a PRN OGTT study visit. At any time point in between study visits, participants experiencing symptoms of diabetes are to contact their clinical trial contact(s). Covid-19 assessments may be completed PRN through the end of the study based on exposure and symptoms.
- Participants are required to receive killed influenza vaccination at least 2 weeks prior to randomization when vaccine for the current or upcoming flu season is available.
- Frequency of CGM blinded, 7-10 day wear will occur at the screening visit, 3 month visit and then semi-annually per schedule of visits.
- Fecal sample: Willing participants will collect fecal samples within +/-3 days of the indicated visit at home and either bring to the research visit or ship samples back to the site. Participants who agree to collect samples should be encouraged to provide samples at all 3 timepoints.
- The bi-annual schedule will continue until the primary endpoint of the study occurs. After the primary endpoint is met, all participants will be followed for an additional year. Participants who develop Stage 3 T1D at any point during the year post-primary endpoint, will be followed for 1 year following their diagnosis.

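### Appendix 2 note 5 ties the month-12 stool sample to Stage 3 visits timed from diagnosis, so unless sites steer those visits most participants diagnosed in the first year lose it.

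*Combined protocol and SAP*

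**What the plan says.** Section 5.3 gives two aims for the stool samples: to "explore whether the gut microbiome can predict response to therapy and whether therapy induces changes in the microbiome". Appendix 1 schedules them at Visit 0, month 3 (V3) and month 12 (V5). Its fecal sample note limits collection to willing participants, encourages them to give all three, and has them collect within 3 days of the indicated visit "at home and either bring to the research visit or ship samples back to the site".

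After a Stage 3 diagnosis the participant moves to Appendix 2, where the Fecal Sample row has no scheduled collection. Note 5 covers those diagnosed less than one year after baseline: a "fecal sample can be collected at a stage 3 visit if the visit occurs" 3 months ± 7 days and/or 12 months ± 14 days after baseline.

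Section 5.5.1 puts Stage 3 visits on a different clock. The first is within 12 weeks of diagnosis. "Study visits will then be completed every six months", within 14 days of a target date counted from that first visit. No section asks sites to time a Stage 3 visit to meet the month-12 stool window.

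**The concern.** The sample is due on a clock that starts at randomization, but may be taken only at visits on a clock that starts at diagnosis. Unless a site aligns them deliberately, the two coincide by chance. Whether the month-12 sample exists then depends on the primary outcome. If ATG delays progression as hoped, a larger share of the placebo arm loses the sample, so the month-12 comparison of microbiome change between arms is selected differently in each arm. A sample not taken at month 12 cannot be recovered later.

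**Working it through.** The documents give no figure for stool-sample loss, so there is none to reproduce. The check works from the design inputs.

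**Inputs**
- Placebo risk, Section 8.4: "progression from Stage 2 (with a 50% 2 year progression risk) to Stage 3 T1D". With exponential times (an assumption), the hazard is ln 2 / 2 = 0.3466 per year.
- Effect, Section 8.4: "a detectable hazard ratio of 0.4". The ATG hazard is 0.4 × 0.3466 = 0.1386 per year.
- Allocation, Section 8.4: 68 ATG, 33 placebo.
- Visit timing, Section 5.5.1: first Stage 3 visit 0 to 84 days after diagnosis, then every six months ± 14 days.
- Month-12 window, Appendix 2 note 5: 28 days wide.
- Also assumed: everyone gives stool and nobody drops out.

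**Step 1: diagnosed before month 12**
- Placebo: 1 − exp(−0.3466) = 29.3%; 33 × 0.293 = 9.7 people.
- ATG: 1 − exp(−0.1386) = 12.9%; 68 × 0.129 = 8.8 people.
- Ratio: 2.26.

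**Step 2: chance that a Stage 3 visit falls in the window, visits not steered**
- A 28-day window against a six-month cycle of about 182.6 days: 28 / 182.6 = 15%.
- Simulation (4 million draws per arm) with the first visit uniform over the 12 weeks, or fixed at 42 or 84 days, agrees: about 85% of early progressors miss the window, in both arms.

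**Step 3: month-12 sample lost, per participant randomized**
- Placebo: 0.293 × 0.85 = 25%, about 8 people.
- ATG: 0.129 × 0.85 = 11%, about 7 people.
- Early progressors would then be about 0.293 × 0.15 / 0.75 = 6% of the placebo participants with a month-12 sample, against 29% of the placebo arm.

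**Step 4: steering**
- If sites use only the ± 14 days on six-monthly visits, about 76% of early progressors still lose the sample (22% of placebo, 10% of ATG).
- If sites also choose the first visit date freely within the 12 weeks, the window is out of reach only for diagnoses at about days 28 to 71 and 211 to 267 after baseline: roughly 99 of 365 days, or 27%. The simulation gives 28%, which is 8% of placebo and 4% of ATG participants.

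**Step 5: detection only at scheduled OGTTs** (month 3 or 6, confirmed 1 to 30 days later; anyone first flagged at month 12 still gives the sample at V5)
- Diagnosed before month 12: 15.9% of placebo, 6.7% of ATG.
- With the first visit uniform over the 12 weeks, lost: 14% and 6%.
- With a fixed delay to the first visit, between 63% (84 days) and 100% (42 days) of early progressors lose the sample.
- With full steering, only about 3% of them do.

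**Step 6: dependence on the hazard ratio**
- The ratio of year-1 diagnosis, placebo to ATG, is 2.97 at a hazard ratio of 0.3, 2.26 at 0.4, 1.84 at 0.5 and 1.0 at 1.0. It exceeds 2 only below about 0.46.

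**Step 7: month-3 sample**
- At risk only in those diagnosed before month 3: 1 − exp(−0.3466 × 0.25) = 8% of placebo and 1 − exp(−0.1386 × 0.25) = 3% of ATG.

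**The case against.** **Sites can steer.** Appendix 1 encourages all three samples, and the 12-week allowance for the first Stage 3 visit leaves room to recover most of them. This stands as a limit on size: the 85% is the unsteered case, not a certainty. But encouragement is not an instruction about visit dates, and full steering still leaves about 28% missing when diagnosis can come at any time.

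**Home collection is also tied to a visit.** A reader might infer that Appendix 1 already frees stool collection from visits, so that note 5 adds a needless condition. It does not: home collection is within 3 days of the indicated visit. Concomitant medications are recorded at study visits (Section 4.6), so a sample shipped between visits would lack that record unless one is added. The fix has to supply it.

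**Samples after diagnosis are confounded.** They come from people with overt hyperglycemia under diabetes management, more of them on placebo. Recovering them therefore replaces some missingness with some confounding. That is fair, but note 5 already accepts such samples, and confounding can be examined when the samples exist and are flagged.

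**Little rests on it.** Collection is voluntary and exploratory. Section 8 names no microbiome endpoint or model, and Section 8.3 describes mechanistic studies from blood draws. This stands in full. No primary, secondary or safety conclusion is affected.

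**Conclusion.** The mismatch of clocks is real and follows directly from Appendix 2 note 5 and Section 5.5.1. With unsteered visits, exponential times, 50% two-year placebo risk and a hazard ratio of 0.4, about 25% of placebo and 11% of ATG participants lose the month-12 sample. The figures are 14% and 6% if diagnosis comes only through scheduled OGTTs, and 8% and 4% if sites fully steer visits. Voluntary uptake lowers the counts but not the ratio if it is equal in the two arms.

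Two stronger readings are not supported. A reader might infer that placebo participants lose the sample more than twice as often as a fixed feature of the rule. That is a rate per participant randomized and needs a hazard ratio below about 0.46. Among early progressors the loss is the same in both arms, the expected counts are close because of the 2:1 allocation, and with no treatment effect there is no imbalance. A reader might also infer that the response-prediction aim is undermined. A month-12 sample taken after diagnosis cannot predict progression; that aim relies on the baseline sample, which note 5 does not touch, and on the month-3 sample, which few can lose.

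What remains is avoidable, outcome-dependent missingness in one exploratory comparison. It is a minor point, worth making because the remedy is cheap.

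**What to change.** Amend Appendix 2 note 5 so that:
- willing participants who progress collect the month-3 and month-12 stool samples at home on the Visit 0 clock, in the V3 and V5 windows, and ship them whether or not a Stage 3 visit falls in the window;
- concomitant medications are recorded at the time of collection, for example at a contact the site is already making (Section 4.8 provides for regular interaction after diagnosis; Appendix 2 has no interim contact row, so the note should name the contact);
- samples taken after Stage 3 diagnosis are flagged, so that the analysis can account for diabetes and insulin.

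Loss caused by this rule then falls to zero in both arms. The cost is an edit to one note, a few more home kits and a brief medication check, with no extra visit. Some samples will be taken after diagnosis, as note 5 already allows.

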APPENDIX 3: Criteria for the Diagnosis of Diabetes⁷

A1C $\geq 6.5\%$ (≥ 48 mmol/mol). The test should be performed in a laboratory using a method that is NGSP certified and standardized to the DCCT assay.*

OR

FPG ≥ 126 mg/dL (≥ 7.0 mmol/L). Fasting is defined as no caloric intake for at least 8 h.*

OR

2-h PG ≥ 200 mg/dL (≥ 11.1 mmol/L) during OGTT. The test should be performed as described by the WHO, using a glucose load containing the equivalent of 75 g anhydrous glucose dissolved in water.*

OR

In an individual with classic symptoms of hyperglycemia or hyperglycemic crisis, a random plasma glucose ≥ 200 mg/dL (≥ 11.1 mmol/L). Random is any time of the day without regard to time since previous meal.

DCCT, Diabetes Control and Complications Trial; FPG, fasting plasma glucose; OGTT, oral glucose tolerance test; NGSP, National Glycohemoglobin Standardization Program; WHO, World Health Organization; 2-h PG, 2-h plasma glucose. *In the absence of unequivocal hyperglycemia, diagnosis requires two abnormal test results obtained at the same time (e.g., A1C and FPG) or at two different time points.

